4.6.2 Expansion Cohort

For all patients, predose (trough) plasma concentrations of emicizumab will be presented descriptively at each timepoint by dose group, including arithmetic and geometric means, median, range, standard deviations, and coefficients of variation.

Nonlinear mixed effects modeling will be used to analyze the dose-concentration-time data of emicizumab following SC administration. Population PK parameters, such as clearance (CL/F) and volume of distribution (V/F), will be estimated, and the influence of various covariates, such as age, gender, and body weight, on these parameters will be

investigated. Secondary PK parameters, such as area under the curve, will be derived from individual post-hoc predictions. Data may be pooled with data from other emicizumab studies and completed Phase III studies. These analyses will be reported in a dedicated report.

4.7 SAFETY ANALYSES

Safety will be assessed through descriptive summaries of adverse events, laboratory test results (serum chemistry and hematology, including complete blood count with differential and platelet counts), ECGs, vital signs, anti-drug antibodies (ADAs), and de novo anti-FVIII inhibitors.

4.7.1 Exposure to Study Medication

Information on study drug administration will be summarized by duration and cumulative dose. In addition, treatment exposure will be summarized, including delays and interruptions. The number of patients whose dose was up-titrated will be summarized. A similar summary will be generated for patients who down-titrate back to 6 mg/kg Q4W, 1.5 mg/kg/QW, or 3 mg/kg Q2W.

Patient withdrawals from study treatment will be reported as listings and summary tables.

4.7.2 Adverse Events

Adverse events will be summarized and presented by System Organ Class mapped term, appropriate thesaurus level, and toxicity grade (WHO Criteria). All adverse events will be coded using the current version of MedDRA at time of database closure. The total number and percentage of patients with at least one adverse event and total number of adverse events will be summarized. Separate adverse event summaries for serious adverse events, adverse events of special interest, severity, relatedness, and discontinuation/modification will be provided.

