All patients, irrespective of the cohort assigned, who continue to derive clinical benefit will be given the opportunity to continue receiving prophylactic emicizumab either within this study or as part of a future extension study according to Roche policy on post-study drug access (see Section 4.3.4). After 24 weeks on prophylactic emicizumab, all patients will be able to continue on their 6 mg/kg Q4W maintenance dose or may be provided the option to increase their dose to 3 mg/kg QW if they meet protocol-defined criteria of suboptimal response. Suboptimal response is defined as follows:

- ≥ 2 qualifying bleeds within 24 weeks while on prophylactic emicizumab

Qualifying bleeds are defined as spontaneous, verified by investigator (e.g., by imaging or physical examination), and occurring while on prophylactic emicizumab at steady state (after the Week 5 visit for expansion cohort/after Week 17 visit for PK run-in cohort). These patients must receive approval from the Medical Monitor to increase their dose to 3 mg/kg QW (see Section 4.3.2).

If the investigator believes that a specific patient warrants dose escalation based on a different reason, he or she may discuss the case with the Medical Monitor for consideration and potential approval.

Upon implementation of protocol Version 5, treatment duration will be extended until 5 years after the last patient is enrolled to enable the collection of additional safety and efficacy data. During this study prolongation, each patient may choose a preferred emicizumab dosing regimen among those permitted (i.e., emicizumab 1.5 mg/kg QW, 3 mg/kg Q2W, or 6 mg/kg Q4W) and continue on that dosing regimen until discontinuation from the study. Instructions for switching the dosing regimen are outlined in Section 4.3.2.1.

Patients who discontinue emicizumab will be followed for 24 weeks after the last emicizumab dose.

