3.2 END OF STUDY AND LENGTH OF STUDY

The end of this study is defined as the date when the last remaining patient has completed the last visit (last patient last visit [LPLV]), as defined by any of the following criteria:

- Completion of at least 24 weeks of emicizumab treatment and either transfer to a separate extension study to receive further emicizumab as per Roche Global Policy on Continued Access to Investigational Medicinal Products *or switch to commercially available product*
OR
- Completion of the end-of-study safety follow-up visit 24 weeks after discontinuing emicizumab
OR
- Withdrawal of consent
OR
- Lost to follow-up

The length of the study for an individual patient will be:

- Screening period up to 4 weeks
- Treatment and observation period at least 24 weeks
- For patients who discontinue emicizumab treatment, safety follow-up visit 24 weeks after discontinuing emicizumab

The total length of the study, from screening of the first patient to the end of the study, is expected to be approximately 6 years.

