Appendix 1 Schedule of Assessments (cont.)

Expansion Cohort																
	Screening		Treatment Period										From Week 25 to Study Completion	Study Completion or Early Termination ^a	Safety Follow-Up Visit	
	Week	Day ^b	1	2	3	4	5	9	13	17	21	25				
	—	—	1	2	3	4	5	9	13	17	21	25				
	-28 to -1	-7 to -1	1	8	15	22	29	57	85	113	141	169				
FVIII or BPA administration during investigational site attendance (e.g., hospitalization or site visit) ^x														After Week 25, blood sample collection for analysis of hemostatic status		

ADA = anti-drug antibody; BPA=bypassing agent; eCRF = electronic Case Report Form; EQ-5D-5L = European Quality of Life 5-Dimension, 5-Level questionnaire; ET = early termination; F/U = follow-up; FIX = factor IX; FVIII = factor VIII; FX = factor X; FXIII = factor XIII; HRQoL = health-related quality of life; PD = pharmacodynamic; PK = pharmacokinetic; PRO = patient-reported outcome; Q4W = every 4 weeks; Q12W = every 12 weeks.

- ^a Study completion visit when either the patient completed 24 weeks' study duration and transferred to an emicizumab extension study OR patient has completed the 24-week safety follow-up visit after emicizumab discontinuation OR patient is lost to follow-up. If study completion occurs after 24 weeks in the study, the completion assessments displayed in the schedule of assessments are similar with the Week 25 visit.
- ^b Assessments can deviate from planned schedule by ± 2 days until safety follow-up visit. Safety follow-up visit should be performed 24 weeks after discontinuation of emicizumab; deviation of +7 days is acceptable. Safety follow-up visit will not be performed for patients who transfer to an extension study or to commercial emicizumab.
- ^c Obtain written informed consent (or patient written assent and legal representative written informed consent if patient is an adolescent) before performing any study related procedures. If a patient fulfills the inclusion criteria, the patient should be enrolled in the study on the same day when the first dose of emicizumab is administered (Day 1).
- ^d Collected from patient's medical record and documented in the eCRF.
- ^e Height assessment at Day 1 only for adults and weight assessments Q4W for all patients.
- ^f Height assessments for adolescents at Day 1 and ideally at all drug administration and PK sampling visits that the patients will be at the investigational site, but at least every 12 weeks (repeated assessments).

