2.5 ANALYSIS TIMING

Analysis on the PK run-in cohort will be conducted 6 weeks after the first 6 patients have completed 6 weeks in the study. This analysis will focus on pharmacokinetics and safety to inform on the opening of the expansion cohort.

The primary analysis will take place at the earliest time when all enrolled patients in the expansion cohort complete 24 weeks in the study or have withdrawn. These analyses will be carried out separately for patients in the expansion cohort and the PK run-in cohort.

The final analysis will occur at the end of the study as defined in the protocol. Additional updates may be performed between the primary and final analyses, as requested by Health Authorities or deemed necessary by the Sponsor.

Additional analyses for Study BO39182 may be conducted to support regulatory submissions.

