4. STATISTICAL METHODS

4.1 OUTPUT LAYOUTS

While the efficacy and safety objectives will primarily be evaluated on the expansion cohort, the same will also be evaluated on the PK run-in cohort at the time of the clinical cutoff to complement the data from the expansion cohort, as applicable. The two key output layouts will therefore be:

- **PK Run-In Cohort:** Includes data from patients enrolled in the PK run-in cohort. This cohort receives 6 mg/kg Q4W without any loading dose.
- **Expansion Cohort:** Includes data from the planned 40 patients who receive 3 mg/kg QW loading dose for 4 weeks followed by 6 mg/kg Q4W.

The output results will be presented in separate tables as below:

| Parameter | Run-In Cohort Total |
|-----------|------------------------|
|-----------|------------------------|

| Parameter | Expansion Cohort Total |
|-----------|---------------------------|
|-----------|---------------------------|

The data under the new, up-titrated or down-titrated dose is analyzed and reported separately. Additional summaries will be produced for key safety and exposure on all data (i.e., data before and after up-titration).

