
Appendix 1

Protocol Synopsis

TITLE: A MULTICENTER, OPEN-LABEL, PHASE III STUDY TO EVALUATE THE EFFICACY, SAFETY, PHARMACOKINETICS AND PHARMACODYNAMICS OF EMICIZUMAB GIVEN EVERY 4 WEEKS (Q4W) IN PATIENTS WITH HEMOPHILIA A

PROTOCOL NUMBER: BO39182

VERSION NUMBER: 2

EUDRACT NUMBER: 2016-001094-33

IND NUMBER: 122954

TEST PRODUCT: Emicizumab (RO5534262)

PHASE: Phase III

INDICATION: Hemophilia A

SPONSOR: F. Hoffmann-La Roche Ltd
Chugai Pharmaceutical Co. Ltd.

Objectives and Endpoints

Pharmacokinetic Run-In Phase Objectives

The objectives of the pharmacokinetic run-in are as follows:

- To investigate the pharmacokinetics of emicizumab after single and multiple (every 4 weeks [Q4W]) subcutaneous (SC) administration of 6 mg/kg
- To assess the safety and tolerability of emicizumab after Q4W SC administration of 6 mg/kg
- To explore the prophylactic effect of emicizumab in maintaining adequate control of bleeding
- To investigate the effect of emicizumab on pharmacodynamic (PD) markers including (but not limited to) aPTT, thrombin generation, and factor VIII (FVIII) activity

Expansion Phase

Efficacy Objectives

The efficacy objectives are as follows:

- To evaluate the efficacy of prophylactic emicizumab in maintaining adequate control of bleeding
- To evaluate *the clinical effect of prophylactic emicizumab on the number of joint bleeds over time*
- To evaluate *the clinical effect of prophylactic emicizumab on the number of target joint bleeds over time (target joints are defined as joints with ≥ 3 bleeds occurring in the same joint over the last 24 weeks prior to study entry)*
- To evaluate *the clinical effect of prophylactic emicizumab on the number of all bleeds (i.e., those treated and untreated with coagulation factors) over time*
- *To evaluate the clinical effect of prophylactic emicizumab on the number of spontaneous bleeds over time (spontaneous bleed rate)*

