- Completion of the end-of-study safety follow-up visit 24 weeks after discontinuing emicizumab

OR

- Withdrawal of consent

OR

- Lost to follow-up

Appendix 1

Protocol Synopsis (cont.)

Length of Study

The length of the study for an individual patient will be:

- Screening period up to 4 weeks
- Treatment and observation period at least 24 weeks
- Safety follow-up visit 24 weeks after discontinuing emicizumab unless patient transfers to a *separate* emicizumab extension study

The total length of the study, from screening of the first patient to the end of the study, is expected to be approximately 20 months.

Investigational Medicinal Products

Test Product (Investigational Drug)

The emicizumab regimen being tested is 3 mg/kg QW for 4 weeks followed by 6 mg/kg Q4W subcutaneously for 24 weeks. All patients with suboptimal control may have the option to increase the dose to 3 mg/kg QW after 24 weeks, with approval from the Medical Monitor

Non-Investigational Medicinal Products

Concomitant therapy includes any medication (e.g., prescription drugs, over-the-counter drugs, herbal or homeopathic remedies, nutritional supplements) used by a patient from 4 weeks prior to screening to the study completion/discontinuation visit. All such medications should be reported to the investigator and recorded on the Concomitant Medications eCRF page.

Concomitant use of the following drugs and therapies will be permitted:

- For patients in the expansion cohort who are on FVIII prophylaxis, they may continue their regular FVIII prophylaxis until the second emicizumab loading dose in order to avoid bleeds before adequate emicizumab level is reached. Concomitant routine FVIII prophylaxis is not otherwise permissible during the study.
- Drugs intended to control bleeds, including FVIII concentrates (*non-inhibitor patients*) or rFVIIa (*inhibitor patients*), should be used at the lowest dose expected to achieve hemostasis. Given that circulating emicizumab may increase patients' coagulation potential, the doses required to achieve hemostasis may be lower than the FVIII or bypassing agent doses used prior to starting the study.

Caution should be taken for patients who are using rFVIIa (e.g., consideration of using no more than 90 µg/kg rFVIIa as an initial dose).

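### SAP 4.7.2 gives adverse events only as crude numbers and percentages, so end-of-study tables under protocol Version 5 will pool patients with very unequal follow-up; add a first-event rate per patient-year

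*SAP*

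**What the plan says.** **Adverse events.** SAP 4.7.2 states: "The total number and percentage of patients with at least one adverse event and total number of adverse events will be summarized". It adds separate summaries for serious events, events of special interest (AESIs), severity, relatedness and discontinuation, without naming another metric. Protocol 6.5 plans incidence by organ class, term level and grade. Neither document gives adverse events a time denominator, a time window or a confidence interval.

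**Time.** SAP 4.7.1 summarises exposure by duration and cumulative dose, and SAP 4.3 evaluates observation time and length of follow-up. SAP 4.1 comes closest to joining safety with time: "Additional summaries will be produced for key safety and exposure on all data (i.e., data before and after up-titration". It names no metric.

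**Bleeds.** SAP 4.5.1 uses the efficacy period as an offset in a negative binomial model and reports a 95% CI.

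**Version and horizon.** The synopsis in SAP Appendix 1 is marked "VERSION NUMBER: 2", and its study length "is expected to be approximately 20 months". In the current protocol, section 3.1.2 says "treatment duration will be extended until 5 years after the last patient is enrolled to enable the collection of additional safety and efficacy data", and section 3.2 expects about 6 years in total. Section 3.2 also lets a patient finish after at least 24 weeks of treatment by moving to an extension study or by a "switch to commercially available product". The extension-study route was already in the Version 2 synopsis; the commercial route is new. On these exits, Protocol Appendix 1 (expansion cohort, footnote b) says: "Safety follow-up visit will not be performed for patients who transfer to an extension study or to commercial emicizumab".

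**Timing.** SAP 2.5: "The final analysis will occur at the end of the study as defined in the protocol". Updates between the primary and final analyses are possible.

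**The concern.** A crude percentage is a fair description when everyone is followed for about the same time. That holds for the planned 24-week analysis. It does not hold at the end of a study in which one patient may leave after 24 weeks and another stay 5 years or more. The percentage then depends on who left and when, as well as on how often events occur. Two data cuts, or this study and another, can differ in crude percentage at the same underlying rate.

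Safety data are among the stated reasons for the extension. Thromboembolic events and thrombotic microangiopathy (TMA) are AESIs, and zero or one case among 40 patients is a plausible result. A bare 0% or 2.5% does not say how much observation stands behind it. The SAP accepts the principle for bleeds but does not carry it over to adverse events.

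**Working it through.** The plan states no figure to reproduce, so the check is an illustration.

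**Inputs.** From the documents: 40 expansion patients (SAP 2), a minimum of 24 weeks of treatment before completion by transfer (Protocol 3.2), and treatment until 5 years after last enrolment (Protocol 3.1.2). Assumed, because the documents do not give them: the share leaving early, the time of leaving (2 years), and constant event rates. Those who stay are counted at 5 years; patients enrolled earlier would have more.

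**1. Spread of follow-up.** 24 weeks = 168/365.25 = 0.460 years, and 5/0.460 gives a 10.9-fold ratio between the shortest completer by transfer and a 5-year patient.

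**2. What the same crude result stands for.** Patient-years (PY) = 2 × leavers + 5 × stayers. For zero events, the exact Poisson upper 95% limit is −ln(0.025)/PY = 3.689/PY. For one event, the exact limits on the count are 0.0253 and 5.572. Expected crude percentage = s(1 − e^(−2r)) + (1 − s)(1 − e^(−5r)), where s is the share leaving and r the yearly rate.

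| Leave at 2 years | PY | 0/40: upper limit per 100 PY | 1/40 (2.5%): rate per 100 PY (95% CI) | Expected crude % at 1 / 2 / 5 per 100 PY |
|---|---|---|---|---|
| 25% | 10×2 + 30×5 = 170 | 2.17 | 0.59 (0.01 to 3.28) | 4.2 / 8.1 / 19.0 |
| 50% | 20×2 + 20×5 = 140 | 2.63 | 0.71 (0.02 to 3.98) | 3.4 / 6.7 / 15.8 |
| 75% | 30×2 + 10×5 = 110 | 3.35 | 0.91 (0.02 to 5.07) | 2.7 / 5.3 / 12.7 |

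Read down the last column: one underlying rate of 2 per 100 PY appears as anything from 8.1% to 5.3%, depending only on the leaving pattern.

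**3. What a reader could recover.** Take the 50% row (140 PY) and divide patients with an event by total observation time.

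- True first-event rate 2 per 100 PY: expected patients with an event = 20(1 − e^(−0.04)) + 20(1 − e^(−0.10)) = 0.78 + 1.90 = 2.69, and 2.69/140 = 1.9 per 100 PY. Almost right.
- Rate 10: 20(1 − e^(−0.2)) + 20(1 − e^(−0.5)) = 3.63 + 7.87 = 11.49, giving 8.2. Too low by about a fifth.
- Rate 50: 20(1 − e^(−1)) + 20(1 − e^(−2.5)) = 12.64 + 18.36 = 31.00, giving 22.1. Less than half the true rate.

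With zero events no time falls after an event, so 3.689 divided by total observation time is exact. For commoner events the shortcut fails, because time after the first event stays in the denominator. Dividing the total event count by time does not help, since it counts repeat events in the same patient.

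**The case against.** The strongest reply is that the planned outputs nearly suffice for rare events. Observation time is to be reported, so anyone can form the zero-event limit, and a one-event rate is hardly moved by time after the event. That stands. A reader might infer that a zero result would be uninterpretable under the present SAP; SAP 4.3 does not support that. What remains is that the SAP does not plan the calculation, and that commoner events such as serious adverse events cannot be treated this way.

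Other points also stand in part.

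- A reader might infer that Version 5 created the 24-week exit. It did not: it added the commercial route and lengthened the upper end.
- A reader might infer that the SAP authors chose badly. The SAP was written for a study of about 20 months, and whether it was later updated cannot be seen from the documents. This is a gap left by the extension.
- A reader might infer that safety and time are never brought together. SAP 4.1 does plan key safety and exposure summaries on all data, though without a metric. That AESIs will be shown only crudely is likewise inferred from the absence of any rate.
- A reader might take the extreme case, with all 40 patients leaving at 24 weeks (18.4 PY and a zero-event limit of 20 per 100 PY), as the likely size. Nothing supports this. Patients who benefit are offered continuation (Protocol 3.1.2), and those already past 24 weeks when Version 5 took effect cannot leave that early by commercial switch.

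Finally, a patient-year rate has limits for these AESIs. Protocol 3.1.2 reports 3 TMA and 2 thromboembolic events in Study BH29884, in patients given repeated aPCC. Years without bypassing agents shrink the upper limit while saying little about risk when aPCC is used. This is a reason to keep case listings beside the rate, but it does not make the crude percentage adequate.

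**Conclusion.** The point holds as a modest one. For the final analysis and any update after Week 24, crude percentages and counts alone leave long-term adverse-event frequency tied to an unstated mix of follow-up times. Under the assumed 2-year leaving pattern the effect is moderate: 5.3% to 8.1% for one underlying rate of 2 per 100 PY, and a zero-event limit of 2.2 to 3.4 per 100 PY. These figures rest on assumed leaving shares, an assumed leaving time and constant rates; the structural point needs only unequal follow-up.

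The study is single-arm and descriptive. No test, planned decision or 24-week result changes. The gain is in how the long-term safety description can be read.

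**What to change.** Update SAP 4.7.2 for protocol Version 5 and keep the crude tables. For the final analysis and any post-Week-24 update:

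1. Add, by cohort, the incidence of first event per 100 patient-years with exact Poisson 95% CIs, for serious adverse events and for each AESI class.
2. Define time at risk as study observation time, not drug exposure. It runs from first dose to the first event of that class, or otherwise to the last study visit, including the safety follow-up visit where one is performed. That visit comes 24 weeks after discontinuation, so a drug-exposure denominator would not match the events counted.
3. Censor at transfer to an extension study or to commercial product. The basis is Protocol 5.3.1, which ends adverse-event reporting at the last study visit, and Appendix 1, which omits the follow-up visit after such a transfer. Protocol 5.4.2.2 and 5.6 do not mention commercial switch, so the SAP should state this rule itself.
4. List each thromboembolic and TMA case with inhibitor status and bypassing-agent and aPCC use, because a constant rate can hide clustering around aPCC.

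The cost is a few extra tables from data already collected. The drawback is that a rate per patient-year assumes a constant hazard, which is why the crude tables and case listings stay beside it.

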4.7.3 Laboratory Data

For clinical laboratory data that were collected from local laboratories, summary statistics will be presented in International System of Units (SI). Laboratory data not collected in SI units will be converted to SI units as applicable. In addition, shift tables describing changes from baseline will be presented using the WHO toxicity grading scale.

Data on the impact of immunogenicity (anti-emicizumab antibodies) on safety, efficacy, and/or clinical pharmacology and pharmacokinetics will be summarized using standard language/terminology ([Shankar et al. 2014](#)).

